### 10.10.2 Body Surface Area Involvement of Psoriasis (BSA)

BSA results will be presented in a by-subject listing.

### 10.10.3 Psoriasis Treatment Convenience Scale (PTCS)

The PTCS consists of 6 disease-specific, self-report questions with a recall period of 1 week and rated on a 1-10 scale.

1. How easy was the treatment to apply to the skin?
2. How greasy was the treatment when applying it to the skin?
3. How moisturised did your skin feel after applying the treatment?
4. How greasy did your skin feel after applying the treatment?
5. How much did treating your skin disrupt your daily routine?
6. Overall, how satisfied were you with the medical treatment?

Each of the questions and the sum of the first 5 questions of PTCS will be summarized using descriptive statistics by treatment for Week 4. Sum of the first 5 question will be further compared between MC2-01 cream and the active comparator using a mixed effect model with treatment as a systematic effect and study site as a random effect. Treatment difference (MC2-01 cream minus active comparator) along with 95% CI will be reported.

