## 7.11 The Psoriasis Treatment Convenience Scale

The Psoriasis Treatment Convenience Scale must be completed by the subjects before any other assessments are performed. The PRO assessments are to be performed as specified in the visit schedule (see [Table 7-2](#), and [Table 7-3](#)).

The aim of the Psoriasis Treatment Convenience Scale is to assess the impact and convenience of psoriasis treatment. The scale has been tested for content validity through focus group interview with 20 patients and adapted based on the responses. The scale consists of 5 disease-specific, self-report questions with a recall period of 1 week and rated on a 1-10 scale.

1. How easy was the treatment to apply to the skin?
2. How greasy was the treatment when applying it to the skin?
3. How moisturised did your skin feel after applying the treatment?
4. How much did treating your skin disrupt your daily routine?
5. Overall, how satisfied were you with the medical treatment?

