	MC2-01 Cream (N=XX)	Active Comparator (N=XX)
Baseline		
Observed Value, n (%)		
N	XX	XX
0 – Clear	XX (XX.X)	XX (XX.X)
1 – Almost clear	XX (XX.X)	XX (XX.X)
2 – Mild	XX (XX.X)	XX (XX.X)
3 – Moderate	XX (XX.X)	XX (XX.X)
4 – Severe	XX (XX.X)	XX (XX.X)
Visit 3/Week 4		
Observed Value, n (%)		
N	XX	XX
0 – Clear	XX (XX.X)	XX (XX.X)
<Etc.>	XX (XX.X)	XX (XX.X)
Change From Baseline, n (%)		
N	XX	XX
2 = Worsen by 2	XX (XX.X)	XX (XX.X)
1 = Worsen by 1	XX (XX.X)	XX (XX.X)
0 = No Change	XX (XX.X)	XX (XX.X)
-1 = Improve by 1	XX (XX.X)	XX (XX.X)
-2 = Improve by 2	XX (XX.X)	XX (XX.X)
-3 = Improve by 3	XX (XX.X)	XX (XX.X)
PGA Treatment Success [1]	XX (XX.X)	XX (XX.X)

[1] PGA success is defined as a minimum 2-point decrease from Baseline in the PGA.

Generated on XX/XX/XX:XXXX by XXXXX / Uses: XXXX / Reference: Data Listings XXXX

Table 14.2.6: Summary of Physician's Global Assessment (PGA)  
Safety Population

	MC2-01 Cream (N=XX)	Active Comparator (N=XX)
Visit 5/Week 8		
Observed Value, n (%)		
N	XX	--
0 – Clear	XX (XX.X)	--
<Etc.>	XX (XX.X)	--
Change From Baseline, n (%)		
N	XX	--
2 = Worsen by 2	XX (XX.X)	--
1 = Worsen by 1	XX (XX.X)	--
0 = No Change	XX (XX.X)	--
-1 = Improve by 1	XX (XX.X)	--
-2 = Improve by 2	XX (XX.X)	--
-3 = Improve by 3	XX (XX.X)	--
PGA Treatment Success [1]	XX (XX.X)	--

[1] PGA success is defined as a minimum 2-point decrease from Baseline in the PGA.

Generated on XX/XX/XX:XXXX by XXXXX / Uses: XXXX / Reference: Data Listings XXXX

Table 14.2.7: Summary of Psoriasis Treatment Convenience Score (PTCS) at Week 4  
Safety Population

	MC2-01 Cream (N=XX)	Active Comparator (N=XX)
Total Score (Sum of Q1 to Q5)		
N	XX	XX
Mean (SD)	XX.X (XX.XX)	XX.X (XX.XX)
Median	XX.X	XX.X
Q1, Q3	XX.X, XX.X	XX.X, XX.X
Minimum, Maximum	XX.X, XX.X	XX.X, XX.X
Linear Mixed Effect Model[1]		
LSM (SE)	XX.X(XX.X)	XX.X(XX.X)
LSM, 95% CI	XX.X, XX.X	XX.X, XX.X
LSM Difference (MC2-01 Cream - Active Comparator) (SE)	XX.X (XX.X)	XX.X (XX.X)
LSM Difference, 95% CI	XX.X, XX.X	XX.X, XX.X
Q1: How easy was the treatment to apply to the skin?		
N	XX	XX
Mean (SD)	XX.X (XX.XX)	XX.X (XX.XX)
Median	XX.X	XX.X
Q1, Q3	XX.X, XX.X	XX.X, XX.X
Minimum, Maximum	XX.X, XX.X	XX.X, XX.X

<<Continue for Q2: How greasy was the treatment when applying it to the skin?

Q3: How moisturized did your skin feel after applying the treatment?

Q4: How greasy did your skin feel after applying the treatment?

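### The PTCS total adds items that point in opposite directions as worded, and neither document gives anchors, reverse scoring or a direction for the total

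*SAP*

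**What the plan says.** SAP 10.10.3 describes the instrument as follows: "The PTCS consists of 6 disease-specific, self-report questions with a recall period of 1 week and rated on a 1-10 scale". Its Q1 is "How easy was the treatment to apply to the skin", its Q2 is "How greasy was the treatment when applying it to the skin" and its Q4 is "How greasy did your skin feel after applying the treatment". Q3 asks how moisturised the skin felt, Q5 how far treatment disrupted the daily routine, and Q6 about overall satisfaction.

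The scoring rule is a sum: "Sum of the first 5 question will be further compared between MC2-01 cream and the active comparator". The model is a mixed model with treatment fixed and site random, and the contrast is cream minus comparator with a 95% CI. The Table 14.2.7 shell repeats the rule as "Total Score (Sum of Q1 to Q5", and Listing 16.2.6.6 carries the same total.

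Protocol 7.11 describes a different instrument: "The scale consists of 5 disease-specific, self-report questions with a recall period of 1 week and rated on a 1-10 scale". It has one greasiness question, and its fifth question is overall satisfaction. Protocol 8.9.2 has the scale summarised and compared between arms but defines no total. SAP section 11, which lists changes from the protocol, deals only with the cortisol criterion.

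**The concern.** A total has a meaning only if every item in it runs the same way. By their wording, more is better on ease and moisturised, and more is worse on the two greasiness items and on disruption. A programmer who follows SAP 10.10.3 literally adds the five raw answers. Gains on one group of items then offset gains on the other.

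Nothing in protocol 7.11, protocol 8.9.2, SAP 10.10.3, the Table 14.2.7 shell or Listing 16.2.6.6 resolves this. None gives the response anchors, a reversal rule, or a statement of whether a higher total is good or bad.

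Apart from the PK ratios, this is the only between-arm comparison for which the SAP specifies a model and a confidence interval. It also bears on the product case in protocol 2.1 and 2.3, where patient preference and convenience are the expected advantages of the cream.

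**Working it through.** The documents give no effect size, power or sample size for the PTCS, so there is no planned figure to reproduce. The check is sign arithmetic on the item wording.

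**Inputs.** Items Q1 to Q5 and the 1-10 range come from SAP 10.10.3. The anchors are not given, so two cases are needed.

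**Case A (assumption): 10 means very much on every item.**

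Let x1 to x5 be the answers.
- Plain sum = x1 + x2 + x3 + x4 + x5.
- Aligned sum = x1 + (11 - x2) + x3 + (11 - x4) + (11 - x5).

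Extremes of the plain sum:
- Best possible answers: 10 + 1 + 10 + 1 + 1 = 23.
- Worst possible answers: 1 + 10 + 1 + 10 + 10 = 32.

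The best answers score lower than the worst. The aligned sum gives 50 and 5.

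Let d1 to d5 be the cream's benefit over the comparator on each item, positive meaning better.
- Aligned difference = d1 + d2 + d3 + d4 + d5.
- Plain difference = d1 - d2 + d3 - d4 - d5.

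The plain difference is zero when d1 + d3 = d2 + d4 + d5, and negative when the right-hand side is larger.

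| Illustrative benefit (d1, d2, d3, d4, d5) | Aligned | Plain sum |
|---|---|---|
| 2, 2, 2, 2, 2 | +10 | 2 - 2 + 2 - 2 - 2 = -2 |
| 1.5, 1, 1.5, 1, 1 | +6 | 1.5 - 1 + 1.5 - 1 - 1 = 0 |
| 0, 2, 0, 2, 0 (greasiness only) | +4 | -2 - 2 = -4 |
| 2, 0, 0, 0, 0 (ease only) | +2 | +2 |

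So the sign can reverse, the effect can vanish, or the two sums can agree, depending on where the benefit lies. These patterns are examples, not forecasts.

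**Case B (assumption): 10 is the favourable end of every item.** The plain sum already equals the aligned sum, and the scoring error is nil.

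**Item list.** Under case A, a uniform 1-point benefit gives 1 - 1 + 1 - 1 - 1 = -1 on the SAP's Q1 to Q5. On a raw sum of the protocol's five items (ease, greasy on applying, moisturised, disruption, satisfaction) it gives 1 - 1 + 1 - 1 + 1 = +1. The choice of items can therefore tip the net direction. Both sets mix directions, however, so the item change is not what causes the cancellation.

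**The case against.** The strongest reply is that the questionnaire itself is not in the documents. If its anchors already put the favourable answer at 10 throughout, the plain sum is right. That stands, and it limits the point. A reader might infer that the planned total is wrong, or that its sign will be wrong; the documents do not support that, because they do not show the anchors. What remains even then is that the SAP never says whether a positive difference favours the cream.

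Second, the SAP summarises every question by arm, Table 14.2.7 shows Q1 to Q6 separately, and Listing 16.2.6.6 gives each subject's answers. A cancelled or reversed total would be partly visible there. This is true, but the item summaries carry no between-arm estimate or interval, so they do not repair the total.

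Third, the PTCS is listed among the Other endpoints in protocol 4.2, in an open-label trial, with no hypothesis or success rule attached. This also stands and keeps the point modest.

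A reader might further infer that the SAP doubled the weight of greasiness relative to the protocol. The documents do not support this: protocol 8.9.2 defines no total, so there was no earlier weight to change, and Q2 and Q4 ask about different moments. Leaving overall satisfaction out of a sum of specific attributes is a defensible choice. Finally, reading a high moisturised answer as favourable is an interpretation, but Q1 and Q2 conflict in wording without it.

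**Conclusion.** The point holds as an unstated scoring direction with a conditional error. If 10 means very much on every item, the stated rule gives 23 to the best answers and 32 to the worst, and a true benefit can cancel or change sign (-2 against +10 for a uniform 2-point benefit). If 10 is best on every item, the sum is valid and only the statement of direction is missing. The benefit sizes are illustrative and come from no document.

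Separately, the six-item SAP scale and the five-item protocol scale disagree, and SAP section 11 does not say so. This is a documentation gap. The content-validity work with 20 patients in protocol 7.11 is reported for a scale described there as having five items.

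The scope is one Other endpoint. The PK, HPA-axis and calcium analyses are unaffected.

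**What to change.** In SAP 10.10.3 and the Table 14.2.7 footnote:

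- State the anchors of each item.
- Before summing, score every item whose high answer is unfavourable as 11 minus the answer. That means Q2, Q4 and Q5, unless the form already anchors 10 as best.
- State that a higher total, and so a positive cream-minus-comparator difference, is favourable.

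In SAP section 11, record that the SAP uses a six-item scale with a total of Q1 to Q5, whereas protocol 7.11 lists five items and protocol 8.9.2 defines no total. Rerunning the mixed model on the protocol's five items is optional.

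The cost is a few sentences, one derivation line and a footnote. Listing 16.2.6.6 shows that all six answers are captured, so no new data are needed. If the SAP is already final, protocol 8.1 requires the change to be described and justified in the trial report.

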## 11. CHANGES FROM THE PROTOCOL AND PLANNED ANALYSES

The 30 minutes ACTH test using the ACTH analogue tetracosactide to stimulate cortisol secretion from the adrenals is an effective test for the assessment of the HPA axis in subjects with pituitary

disease. Diagnostic criteria for adrenal insufficiency have traditionally relied both on the absolute level of cortisol 30 minutes after injection of tetracosactide as well as a requirement of an absolute increase in cortisol during the test. The diagnostic criteria used in the MC2-01-C3 protocol was based on the USPI dated February 2012 (1) for Cosyntropin in which there were specific requirements to plasma cortisol both concerning the level of increase as well as the 30 minutes value according to the original description of the test (2) when testing morning samples. The diagnostic value of an absolute increase in cortisol has, however, been challenged. Several studies, e.g.(3, 4) have shown that calculation of the increment cortisol increase is of no diagnostic value, and careful reviews (5, 6) have strongly warned against this parameter as a diagnostic criterion. As a consequence, both expert guidelines from the Endocrine Society (7) as well as the recently updated (May 2018) USPI for Cosyntropin (8) recommends the 30 minutes cortisol value as the sole diagnostic criterion for the diagnosis of adrenal insufficiency with a limit for adrenal suppression of plasma cortisol < 18 µg/dl (500 nmol). This criterion is used in the evaluation of the data obtained in MC2-01-C3 trial. Furthermore, the plasma cortisol from the ACTH challenge test is measured by mass spectrometry. Mass spectrometry assays of cortisol are without any of the positive bias that plague most cortisol immunoassays (9) and consequently limit for adrenal suppression of plasma cortisol is below 14 µg/dl (390 nmol/l) according to laboratory report from the manufacturer (Quest Diagnostics) of this test. For this reason, this lower limit for plasma cortisol of 14 µg/dl (390 nmol/l) will also be used in the evaluation of the data obtained in MC2-01-C3 trial.

1. FDA. Cosyntropin USPI Sandoz. 2012.

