Investigational Product(s):	MC2-01 cream (CAL and BDP, w/w 0.005%/ 0.064%).
Reference Product(s):	CAL/BDP ointment (w/w 0.005%/0.064%). Approved in the United States (US) as Taclonex® Ointment and in rest of the world as Daivobet® Ointment/Dovobet® Ointment.
Pharmacokinetics Evaluation Criteria:	
Blood samples for PK assessments will be collected at
 
 
• SV2 (baseline sample)
 
• Week 2
 
• Week 4 and for subjects assigned to the MC2-01 cream at Week 8; before application of trial medication and then at 0.5, 1, 2, 3, 5, and 7 hours after the application.
 
 
The samples will be assayed for concentrations of the active ingredients (BDP and CAL) and for their main metabolites; betamethasone 17-propionate and MC1080, respectively.

HPA axis and calcium metabolism Evaluation Criteria:	
For subjects assigned to the MC2-01 cream, the endpoint for the HPA axis evaluation will be a serum cortisol level of 18 µg/dL or less at 30 minutes after ACTH challenge at Week 4 and Week 8:
 
The primary response criteria for calcium metabolism will be changes from Baseline to Week 4 and Week 8 in:
 
 
• Albumin-corrected serum calcium;
 
• 24-hour urinary calcium excretion;
 
• Ratio of urinary calcium to creatinine.
 

Other Safety Evaluation Criteria	Adverse event incidence and severity, laboratory test results (haematology, clinical chemistry, urinalysis), vital signs, local skin reactions, physical examination. For subjects assigned to the MC2-01 cream electrocardiogram (ECG).

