#### **Secondary Endpoints**

##### HPA axis evaluation for subjects assigned to the MC2-01 cream:

The number of subjects with a serum cortisol level of 18  $\mu\text{g}/\text{dL}$  or less at 30 minutes after ACTH challenge at Week 4 or Week 8.

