### 7.9.2 HPA axis suppression/ ACTH challenge test

For subjects assigned to the MC2-01 cream, adrenal function will be assessed in a challenge test with an intravenous dose of adrenocorticotropic hormone (ACTH) (cosyntropin). Measurement of serum cortisol levels pre- and post- stimulation with cosyntropin 0.25 mg is the accepted standard method used to evaluate adrenal suppression. The ACTH challenge test will be performed at Visit 1/Day 0, Week 4 and Week 8 visits. The test consists of blood sampling starting at 8 am ( $\pm$  30 minutes). Following the blood sample, an intravenous bolus injection of 0.25 mg cosyntropin is given at time zero (t=0 minutes). Serum cortisol concentration at t=30 minutes will reflect

stimulation of the adrenal glands induced by cosyntropin. The ACTH challenge test must be performed before application of the IP.

Since many people do not respond to the degree expected with cosyntropin stimulation, the following criteria have been established to denote a normal response:

1. pre-stimulation cortisol levels  $>5 \mu\text{g/dL}$  will be considered normal,
2. the 30-minute post-stimulation level should show an increment of  $\geq 7 \mu\text{g/dL}$  above the basal level, and
3. the 30-minute post-stimulation level should exceed  $18 \mu\text{g/dL}$ .

Therefore, a basal serum cortisol level  $\leq 5 \mu\text{g/dL}$ , or a 30-minute post-stimulation level  $\leq 18 \mu\text{g/dL}$ , or a post-stimulation increase (over basal)  $< 7 \mu\text{g/dL}$  constitutes the definition of HPA axis suppression in the trial.

Visit 1/Day 0: If HPA axis is suppressed at Visit 1/Day 0, the subject should be contacted because the application with the investigational product (IP) should be discontinued and an Early Termination visit should be performed (see [Section 7.16](#)).

Week 4: If HPA axis is suppressed at Week 4, the subject should be contacted and the application with the MC2-01 cream should be discontinued. The subject should continue in the trial and the ACTH challenge test is repeated at the Week 8 visit. If HPA axis suppression is noted at Week 8, the subject must return for a follow-up visit (see [Section 7.15](#)).

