## 10.8 Safety Analysis

### 10.8.1 Safety Endpoints

Primary safety endpoints include:

- HPA-axis suppression

HPA-axis function will be assessed in a challenge test with an intravenous dose of adrenocorticotropic hormone (ACTH) (Cosyntropin). **Normal HPA function** is, based on the Cosyntropin US Packing Insert (USPI) (revision May 2018), defined as a 30-minute post-stimulation cortisol level  $\geq 18 \mu\text{g/dL}$ .

Conversely, **HPA-axis suppression** is defined as 30-minute post-stimulation cortisol level <18 µg/dL.

HPA-axis function status will be considered as missing if post-stimulation serum cortisol level is missing.

- Changes in calcium metabolism endpoints from 24-hour urinalysis, including
  - Albumin-corrected serum calcium
  - 24 hours urinary calcium excretion
  - Ratio of urinary calcium to creatinine

Other safety endpoints include:

- Adverse events (AEs)
- Local Skin Reaction (LSR) Assessment
  - Investigator assessed signs: erythema, scaling, edema, atrophy, vesicles and erosion/ulceration; vesicles, and erosion/ulceration
  - Subject assessed symptoms: burning or pain
- Laboratory parameters
  - Hematology: hemoglobin, hematocrit, red blood cell (RBC) count, mean corpuscular volume (MCV), white blood cell (WBC) count, including differential count and platelet count.
  - Serum biochemistry: cortisol, urea, glucose, creatinine, calcium, albumin, calcium (albumin corrected), sodium, potassium, chloride, calcium, phosphate, alkaline phosphatase (ALP), plasma parathyroid hormone (PTH), 25-OH Vitamin D (Visit 1 only)
  - 24-hour urinalysis: calcium, phosphate, creatinine, volume, total calcium excretion, total phosphate excretion, total creatinine excretion, urinary calcium:creatinine ratio, urinary phosphate:creatinine ratio
- Vital signs (blood pressure, pulse rate)
- Standard 12-lead electrocardiogram (ECG) (MC2-01 cream subjects only)
- Physical examination (PE)

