## 10.8.2 Analyses of Safety Endpoints

### 10.8.2.1 HPA-axis Suppression

The number and proportion of subjects with HPA-axis suppression at Week 4 will be summarised for the HPA population. Subjects with HPA-axis suppression at Week 4, was as described in the

protocol, contacted to discontinue use of MC2-01 cream. Subjects with HPA-axis suppression at Week 8 will be summarised overall and separately by HPA-axis suppression status at Week 4.

An additional analysis of the number and proportion of subjects with HPA-axis suppression will be summarised based on the test laboratory normal reference range established for the analytical method used by the test laboratory in the trial for the ACTH challenge test.

- In this analysis HPA suppression is defined as a 30-minute post-stimulation cortisol level  $< 14 \mu\text{g/dl}$  (test laboratory normal reference range of 14 to 36  $\mu\text{g/dl}$  for the 30-minute post-stimulation cortisol level). This analysis will be performed among MC2-01 cream subjects whose Baseline cortisol level is  $\geq 14 \mu\text{g/dl}$

All HPA-axis function test results (baseline, Week 4, Week 8, and Follow-up) will be presented in a by-subject listing for the Safety population.

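### No planned table summarises the three-criterion HPA suppression definition that stops cream at Week 4, and the protocol's own endpoint differs from that definition

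*SAP*

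**What the plan says.** The protocol gives two definitions. In the synopsis, "the endpoint for the HPA axis evaluation will be a serum cortisol level of 18" µg/dL or less, 30 minutes after ACTH challenge. Section 4.2 repeats this as the secondary endpoint: "The number of subjects with a serum cortisol level of 18" µg/dL or less. Section 7.9.2 lists three criteria (basal ≤5, 30-minute ≤18, or increment <7) and says that meeting any one "constitutes the definition of HPA axis suppression in the trial". The same section acts on it: suppression at Day 0 leads to discontinuation and an Early Termination visit. Suppression at Week 4 leads to discontinuation of cream, with the subject kept in the trial and retested at Week 8.

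SAP 10.8.1 keeps one criterion, "based on the Cosyntropin US Packing Insert (USPI) (revision May 2018": suppression "is defined as 30-minute post-stimulation cortisol level <18" µg/dL. SAP section 8 selects the HPA population by Baseline 30-minute cortisol ≥18. SAP 10.8.2.1 adds one further version: "An additional analysis of the number and proportion of subjects with HPA-axis suppression will be summarised based on the test laboratory normal reference range", with a cut-off of <14. Tables 14.2.4.1 and 14.2.4.2 carry these two cut-offs only. Section 11 explains the change and says of the <18 rule: "This criterion is used in the evaluation of the data obtained in MC2-01-C3 trial".

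**The concern.** The rule that stopped treatment and the rule that counts suppression are not the same. A subject can be taken off cream at Week 4 as suppressed under 7.9.2 and then be reported as not suppressed at Week 4. The SAP splits Week 8 results by Week 4 status, directly after noting that suppressed subjects were told to stop, so that split will not cleanly separate subjects still on cream from those off it.

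Both SAP cut-offs are narrower than 7.9.2. A reader of the tables would see two versions of the rate, neither by the definition that governed conduct, and could not tell from them how much of a low rate is due to the choice of definition. This is the secondary objective of a maximum-use trial with about 25 to 30 cream subjects, so a few reclassified subjects matter.

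**Working it through.** Neither document states an expected suppression rate, so there is no planned figure to reproduce. Write b for basal and p for 30-minute cortisol, in µg/dL.

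**Inputs**
- Protocol 7.9.2: b ≤5 or p ≤18 or p − b <7
- Protocol synopsis and 4.2: p ≤18
- SAP 10.8.1: p <18
- SAP 10.8.2.1, additional analysis: p <14
- Baseline filter: not suppressed (Protocol 8.3, read with 7.9.2); p ≥18 (SAP section 8)

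**Step 1: same tested subjects.** p <14 implies p <18, which implies p ≤18, which is one of the three criteria. The sets are nested, so the SAP count is equal to or below the 7.9.2 count. Against 4.2, the SAP differs only at exactly 18.0.

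| b | p | p − b | 7.9.2 | 4.2 | SAP <18 | SAP <14 |
|---|---|---|---|---|---|---|
| 14 | 20 | 6 | yes | no | no | no |
| 4.5 | 20 | 15.5 | yes | no | no | no |
| 10 | 18.0 | 8 | yes | yes | no | no |
| 10 | 17.9 | 7.9 | yes | yes | yes | no |
| 10 | 13.5 | 3.5 | yes | yes | yes | yes |

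**Step 2: the denominator also moves.** The SAP filter admits subjects who fail 7.9.2 at Baseline only on the basal or increment criterion. If they are tested at Week 4, the rate can rise. For example, take 2/20 = 10% under 7.9.2. Admit five more subjects, three of them with p <18 at Week 4, and the SAP rate is (2 + 3)/(20 + 5) = 5/25 = 20%. If instead they stopped at Day 0 as 7.9.2 requires and had no Week 4 test, the tested subjects are the same under both filters and Step 1 applies.

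**Step 3: Week 8.** Take the first row of the table at Week 4. Under 7.9.2 the subject stops cream. Under the SAP the subject is not suppressed at Week 4 and so falls on that side of the Week 8 split, after about four weeks off cream. The programming note also sets the denominator of both split rows to subjects suppressed at Week 8, so neither row is a rate among subjects who continued or stopped.

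**Step 4: illustrative size.** Assume p is normal, with the laboratory range 14 to 36 as its central 95%: mean (14 + 36)/2 = 25, SD (36 − 14)/(2 × 1.96) = 5.6. Then P(p <18) = Φ((18 − 25)/5.6) = Φ(−1.25) = 10.6%, and P(p <14) = Φ(−1.96) = 2.5%. Assume further a basal mean of 10 to 14 with SD 4, a correlation of basal with 30-minute cortisol of 0.3 to 0.7, a between-visit correlation of 0.5 to 0.7, and no drug effect. None of these further values has a basis in the documents. By simulation, with each definition applied to its own Baseline-normal population:
- Smallest gap (basal mean 12, both correlations 0.7): 8.8% by 7.9.2 and 6.2% by the SAP; 25 × 0.026 ≈ 0.7 subjects.
- Largest gap (basal mean 14, within-visit correlation 0.3, between-visit 0.5): 19.5% and 7.9%; 25 × 0.116 = 2.9 subjects.

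**Step 5: what a few subjects do.** At n = 25 (the per-arm PK target, used here as a round figure) each subject moves the rate by 1/25 = 4 points. Exact 95% limits are 0% to 13.7% for 0/25 and 2.5% to 31.2% for 3/25 = 12%.

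**The case against.** The strongest reply is that the declared endpoint was always the 30-minute value alone, and that the SAP departs from it only at exactly 18.0. That stands: the root problem is a conflict inside the protocol. It is not a complete answer. Protocol 8.8 says suppression is assessed from pre- and post-stimulation cortisol, 8.8.1 summarises HPA-axis suppression, which 7.9.2 defines, and SAP section 11 itself presents the single criterion as a change.

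Second, the change is disclosed and argued, with a revised label, a guideline and the assay method as reasons. That also stands, and nothing here disputes those reasons. But section 11 argues about the increment and never names the basal criterion it also drops. It is silent on the conflict between 4.2 and 7.9.2 and on the mismatch with the stopping rule.

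Third, Listing 16.2.6.7 shows pre- and post-stimulation values, so 7.9.2 status can be rebuilt by hand. True: a summary is missing, not the data.

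Two stronger readings are tempting. One is that the definition was changed after Week 4 results were known. The trial is open-label, the May 2018 label falls inside the planned trial period, and SAP 10.8.2.1 uses the past tense ("Subjects with HPA-axis suppression at Week 4, was as described in the" protocol, contacted to stop). This suggests that Week 4 results existed but does not prove it. The text available carries no SAP date, its title pages being absent; nothing says that the authors had reviewed cortisol values; and Protocol 2.2 also slips into the past tense for a planned restriction. The other is that the rate can only fall. Step 2 shows that this holds for the same tested subjects, not in general.

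**Conclusion.** The point holds as a gap in reporting and a mismatch between conduct and analysis. No planned table summarises suppression as 7.9.2 defines it, although that definition decided who stopped cream. In the same tested subjects the SAP count is equal or lower. Because the Baseline filter is relaxed too, the rate could rise if the extra subjects were tested. Subjects stopped for basal or increment reasons with 30-minute cortisol ≥18 are misplaced in the Week 8 split; this does not depend on motive or timing.

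The size is about 0.7 to 2.9 more suppressed subjects per 25 under 7.9.2. It is an illustration only: it rests on normality, on reading the laboratory range as a central 95%, and on assumed basal levels, correlations and no drug effect. The documents do not establish a results-driven redefinition, and the point does not need one. A change is advisable; the main analysis need not be replaced.

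**What to change.** Keep the SAP main analysis and make these additions:

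1. Beside Tables 14.2.4.1 and 14.2.4.2, add one sensitivity table with the number and proportion suppressed at Week 4 and Week 8 by the 7.9.2 definition, used for both the Baseline population and the outcome. State that the denominator is subjects tested at the visit.
2. Cross-tabulate subjects actually stopped at Week 4 against their SAP Week 4 status, and show Week 8 results by whether cream was continued.
3. In SAP section 11, give the date of the definition change relative to availability of cortisol results. Note that the basal criterion is dropped as well, and that Protocol 4.2 and 7.9.2 differ and must be reconciled.

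The cortisol values are already in Listing 16.2.6.7 and the approved stop dates in Listing 16.2.5.1, so the cost is one extra table, a small cross-tabulation and a few sentences. The downside for the sponsor is that a less favourable rate may appear beside the main one.
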